### 6.2.2 Supportive secondary efficacy endpoints

- Additional analysis for changes from baseline at 16 and 52 weeks
  - BMI SDS (%)
  - BMI (%)

It will be analysed with the same type of ANCOVA with MI as used for the main analysis of the primary endpoint, with the corresponding baseline covariate.

- During the blinded review of data it has been observed that there were only few subjects achieving  $\geq 10\%$  reduction in baseline BMI at week 16 or at week 52 (as mentioned in section [5.4.1](#)). Therefore the statistical analysis (J2R-MI Logistic Regression) will not be performed for this endpoint and will be summarised descriptively.
- For the analysis of categorical endpoints , the protocol mentions to include treatment, sex, region, baseline glycaemic category, stratification factor for Tanner stage and interaction between baseline glycaemic category and stratification factor for Tanner stage as fixed effects, and baseline BMI/BMI SDS (wherever applicable) and baseline age as covariates. During the blinded review of data for the categorical endpoints it has been observed that due to the small number of subjects in the trial the model cannot be estimated. To avoid the risk of over fitting and to make the model estimable the following explanatory variables will be removed from the analysis model.: sex, region ,interaction between baseline glycaemic category and stratification factor for Tanner stage.
- During the blinded review of data it has been observed that no subject reported an amylase measurement above 3UNR and only one subject reported a lipase measurement above 3UNR. Due to the few number of subjects having a measurement above 3UNR,for these parameters at any time during treatment, the statistical analysis (Logistic Regression) will not be performed.

### 6.2.3 Supportive secondary safety endpoints

- Additional safety endpoints, is been added as below.
  - Height velocity in cm/year (if subject is still growing)
- The testosterone analysis (change from baseline values at week 16 and 52) for part B could not be performed as originally planned due to an unforeseen change in the assay used by the central laboratory to measure testosterone during the trial. On 05 Dec 2018, Q2 laboratories moved from the Siemens ADVIA Centaur Testosterone “TSTO” assay to the new “TSTII” assay. The upgraded assay adheres more closely to the LC-MS reference values. This change in methodology prevented a direct comparison of values measured at different time points during the trial. As a result, the changes from baseline for individual subjects at week 16 and 52 are not provided for part B. Testosterone analysis for part A will be performed as mentioned in protocol. A listing of various hormones (LH, FSH and testosterone) analysed at different timepoints during the trial will be provided with reference ranges. Summary statistics for the testosterone analysis using the two different assays will be provided.
- Safety analysis set will be used to analyse change from baseline pulse values at week 16 and 52. Also to analyse MMRM model for relative change from baseline for amylase and lipase values at week 16 and 52.
- C-SSRS will only be summarised using summary statistics (frequency count, percentage) for baseline, week 16 and week 52 and the shift from baseline to 16 and 52 week will not be produced.

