#### 4.2.2.3 Supportive secondary safety endpoints

- Number of treatment-emergent adverse events during the trial
- Number of severe treatment emergent episodes of hypoglycaemia
- Number of blood glucose confirmed symptomatic episodes of hypoglycaemia
- Occurrence of anti-liraglutide antibodies

Change from baseline to 16 and 52 weeks in:

- Electrocardiogram (ECG)
- Pulse
- Laboratory parameters:
  - Haematology: haemoglobin, haematocrit, thrombocytes, erythrocytes, leukocytes, differential count (eosinophils, neutrophils, basophils, lymphocytes, monocytes)
  - Biochemistry: creatinine, creatine kinase (CPK), urea, albumin, bilirubin (total), alanine aminotransferase (ALT), aspartate aminotransferase (AST), alkaline phosphatase, sodium, potassium, calcium total, calcium albumin corrected, amylase, lipase, and carcinoembryonic antigen (CEA)
  - Hormone levels including: calcitonin, insulin-like growth factor-1 (IGF-1), thyroid stimulating hormone (TSH), free thyroxine (free T4), prolactin, adrenocorticotrophic

Protocol: Liraglutide  
Trial ID: NN8022-4179  
UTN: U1111-1162-7884  
EudraCT no.: 2014-004415-37

~~CONFIDENTIAL~~

Date:	16 July 2020	Novo Nordisk
Version:	5.0	
Status:	Final	
Page:	27 of 125	

hormone (ACTH), cortisol, dehydroepiandrosterone sulfate (DHEAS), luteinising hormone (LH), follicle stimulating hormone (FSH), estradiol (females), testosterone (males)

- Pubertal status
- Physical examination including height
- Part A only: Mental health assessed by Columbia Suicidality Severity Rating Scale (C-SSRS) and Patient Reported Health Questionnaire-9 (PHQ-9)

\*Key supportive secondary endpoint prospectively selected for posting on clinicaltrials.gov and EudraCT)

Protocol: Liraglutide  
 Trial ID: NN8022-4179  
 UTN: U1111-1162-7884  
 EudraCT no.: 2014-004415-37

[figure not shown]
CONFIDENTIAL

Date: 16 July 2020  
 Version: 5.0  
 Status: Final  
 Page: 28 of 125  
 Novo Nordisk

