Subjects with a history of acute or chronic pancreatitis will be excluded from trial participation. Trial participants will be informed of the characteristic symptoms of acute pancreatitis. Furthermore, serum lipase and amylase activity levels will be monitored on a regular basis during the course of the trial. If pancreatitis is suspected, liraglutide/liraglutide placebo will be discontinued until confirmatory tests have been conducted and appropriate treatment should be initiated. Subjects that are diagnosed with acute pancreatitis must have their trial product withdrawn.

Subjects with a personal or family history of MTC and subjects with Multiple Endocrine Neoplasia Syndrome type 2 are excluded from this trial. In addition, subjects with a screening calcitonin (a specific biomarker for C-cell activation) level  $\geq 50$  ng/L will be excluded from the trial, as hormone concentrations above this threshold are indicative of C-cell neoplasia. During the trial, calcitonin levels will be measured at pre-specified trial visits and levels above upper normal range will be flagged by the laboratory, and reported to the investigator and Novo Nordisk.

It is assumed that the benefits and risks associated with long-term liraglutide treatment will be the same for the paediatric population with PWS as for the adult populations with the exception of any unforeseen effects on growth and pubertal development. In non-clinical studies, dosing liraglutide from post-natal day 21 to 91 in juvenile rats caused a dose-dependent delay in sexual maturation,

Protocol: Liraglutide  
Trial ID: NN8022-4179  
UTN: U1111-1162-7884  
EudraCT no.: 2014-004415-37

CONFIDENTIAL

Date: 16 July 2020  
Version: 5.0  
Status: Final  
Page: 106 of 125

Novo Nordisk

defined in females as age of animals for vaginal opening, and for males as preputial separation (both onset and end) that was most pronounced in females. A delay in age of sexual maturation is known to occur in rats and humans under caloric restriction/increased energy expenditure. Estrous cycle length was slightly extended among high-dose female rats during treatment but returned to normal after two weeks of recovery.

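### SAP 6.2.3 withholds testosterone change from baseline for every Part B boy, although the 5 December 2018 assay switch invalidates only pairs of samples that straddle that date

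*SAP*

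**What the plan says.** Protocol 4.2.2.3 lists change from baseline to weeks 16 and 52 in laboratory parameters as supportive secondary safety endpoints. Testosterone is one of the hormones and is measured in males only.

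SAP 6.2.3 records a departure from that plan. It dates the event ("On 05 Dec 2018, Q2 laboratories moved from the Siemens ADVIA Centaur Testosterone", to a newer version of the assay) and gives the reason: "This change in methodology prevented a direct comparison of values measured at different time points during the trial". The consequence is that "the changes from baseline for individual subjects at week 16 and 52 are not provided for part B". No exception is made for subjects whose samples were all run on one assay.

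The same section keeps three things:

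- Part A testosterone stays as the protocol planned it.
- Individual values are still to be shown: "A listing of various hormones (LH, FSH and testosterone) analysed at different timepoints during the trial will be provided with reference ranges".
- Testosterone is also to be summarised descriptively under each of the two assays.

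SAP 5.4.1.3 also keeps changes in Tanner stage at weeks 16 and 52, and baseline shifts for the laboratory parameters.

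**The concern.** The rule is wider than its reason. An assay change spoils a difference only when the two values come from different assays. A boy randomised on or after 5 December 2018 has every sample on the new assay. A boy who reached week 16 before that date has baseline and week 16 on the old one. Neither is affected by the stated problem, yet both lose their change from baseline.

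Part B enrols the children below Tanner stage 2. Protocol 18.1 treats unforeseen effects on growth and pubertal development as the exception to its assumption that paediatric risks match adult ones. It cites juvenile rats, in which dosing "caused a dose-dependent delay in sexual maturation". Paired change is the direct descriptive summary of a hormone in so small a group.

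The by-assay summaries do not replace it. On the planned dates every week-52 value is on the new assay, but only boys randomised after the switch have a new-assay baseline. Setting the new-assay week-52 mean against the new-assay baseline mean would compare different sets of boys.

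**Working it through.** **Inputs**

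- Switch date: 5 December 2018 (SAP 6.2.3).
- Planned Part B first visits 9 April 2018 to 1 July 2019, stated as 64 weeks; planned first treatments 23 April 2018 to 15 July 2019 (Protocol 7.2).
- Part B size 24, split 16 to 8, with 17 (minimum) to 19 (expected) completers (Protocol Table 17-2).
- Testosterone in boys only (Protocol flow chart, footnote 7).
- Central-laboratory samples are analysed as they arrive (Protocol 8.2), so the sample date indicates the assay.
- Assumptions: even accrual; baseline on the day of first treatment; week 16 = +112 days; week 52 = +364 days; 50% boys (range 30 to 70%).

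**Plan's own figure.** 9 April 2018 to 1 July 2019 is 448 days, and 448/7 = 64.0 weeks, as stated. The first-treatment window is also 448 days.

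**Classification by first-treatment date**

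1. All samples on the new assay: 5 December 2018 to 15 July 2019 = 222 days; 222/448 = 49.6%.
2. Baseline and week 16 both on the old assay: first treatment before 5 December 2018 − 112 days = 15 August 2018. From 23 April that is 114 days; 114/448 = 25.4%.
3. Straddling at week 16: 448 − 222 − 114 = 112 days; 112/448 = 25.0%.
4. Baseline and week 52 both on the old assay: first treatment before 5 December 2018 − 364 days = 6 December 2017, earlier than the window opens. None.

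**Same-assay pairs among 24 subjects**

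- Week 16: (222 + 114)/448 = 75.0%; 0.75 × 24 = 18.
- Week 52: 222/448 = 49.6%; 0.496 × 24 = 11.9.

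**Boys with a same-assay pair, before dropout**

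| Share of boys (assumed) | Week 16 | Week 52 |
|---|---|---|
| 30% | 5.4 | 3.6 |
| 50% | 9.0 | 5.9 |
| 70% | 12.6 | 8.3 |

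At 50% boys, the 9 at week 16 are about 3 on the old assay (roughly 2 liraglutide, 1 placebo) and 6 on the new (4 and 2). The 6 at week 52 fall to between 5.9 × 17/24 = 4.2 and 5.9 × 19/24 = 4.7 after dropout.

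**Sensitivity to accrual (last first treatment moved; assumed dates)**

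- To 1 December 2019 (587 days): week 16 (361 + 114)/587 = 80.9%; week 52 361/587 = 61.5%.
- To 1 March 2019 (312 days): week 16 (86 + 114)/312 = 64.1%; week 52 86/312 = 27.6%.

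**Support that does not use planned dates.** SAP 5.3.2.2 says that pandemic disruption affected a few Part B week-16 or week-52 visits. The SAP does not date the disruption. If it began no earlier than 4 December 2019 (5 December 2018 + 364 days; assumed), any affected visit belongs to a subject randomised on or after the switch, apart from a few days of visit window. This shows that post-switch subjects exist. It does not show how many are boys with both samples.

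**The case against.** A reader might infer that Part B loses its puberty-safety assessment, or testosterone altogether. The documents do not support that. What goes is one derived quantity for one analyte, in boys, in one part of the trial. Testosterone values by time point stay in the listing with reference ranges, both assays are summarised, and Part A proceeds as planned. LH, FSH, estradiol and Tanner stage are untouched. Protocol 8.5.9 also requires testicular volume in boys and adverse event reporting of accelerated puberty. It would be equally wrong to say that the whole restriction is needless: for boys who straddle the switch, withholding the change is right.

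The link to the animal finding also needs qualifying. Protocol 18.1 says that males were affected but that the delay was most pronounced in females, in whom testosterone is not measured.

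The best remaining argument is that the listing already holds the information and that cells of about 1 to 4 boys barely merit a table. This has force. A same-assay change could be worked out from the listing, but only if the assay is identifiable there, and the SAP does not say that it will be. Leaving readers to pair values by hand is a poor substitute for reporting them.

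The shares cannot be verified, because actual randomisation dates and the number of boys are not given. Nor does the flow chart, as extracted, clearly show a week-16 hormone sample. That is probably a broken table: SAP 6.2.3 itself describes the planned analysis as covering week 16, and Protocol Table 8-1 gives Visit 10 the largest blood draw, 29.0 mL.

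**Conclusion.** The point holds in limited form. SAP 6.2.3 withholds Part B testosterone change for all boys on a ground that covers only straddling pairs: on the planned dates about 25% of subjects at week 16 and about 50% at week 52. What is lost is the within-subject change for same-assay boys, about 9 (5 to 13) at week 16 and 6 (4 to 8) at week 52 before dropout. These counts are illustrative. They rest on planned dates, even accrual and an assumed 30 to 70% share of boys; accrual later than planned would raise both shares and accrual that ended sooner would lower them.

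This is a minor reporting improvement. Testosterone is a supportive safety parameter reported descriptively, so no hypothesis test is involved.

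**What to change.** Add one sentence to SAP 6.2.3: for Part B boys whose baseline and later samples were run on the same assay, change in testosterone from baseline to weeks 16 and 52 will be reported descriptively, by treatment and labelled by assay, with the number excluded for straddling the switch stated at each visit. Keep the planned listing and by-assay summaries for all boys, and show the assay beside each testosterone value in the listing. Where the laboratory's assay code is held, filter on that in preference to sample date, since a sample drawn just before the switch may have been run after it.

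The cost is that sentence and one filter; no new data are needed. The downside is very small cells, so the output should be descriptive only. If they are too small for a table, a same-assay change column in the planned listing would serve.

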## 6.3 Appendix 3: Definition and calculation of endpoints, assessments and derivations

### 6.3.1 Endpoint derivations and assessments

#### 6.3.1.1 BMI Standard deviation score (BMI SDS) and Height Standard deviation score (Height SDS)

BMI SDS and height SDS score will be calculated using external reference data on BMI and height from WHO

The following procedure is recommended to calculate a z-score for an individual child with measurement  $y$  at age  $t$ :

1: Calculate

$$Z_{\text{ind}} = \frac{[y/M(t)]L(t) - 1}{S(t) L(t)}$$

2: Compute the final z-score ( $Z_{ind}^*$ ) of the child for the indicator as:

$$z_{ind}^* = \begin{cases} z_{ind} & \text{if } |z_{ind}| \leq 3 \\ 3 + \left( \frac{y - SD3pos}{SD23pos} \right) & \text{if } z_{ind} > 3 \\ -3 + \left( \frac{y - SD3neg}{SD23neg} \right) & \text{if } z_{ind} < -3 \end{cases}$$

Where:

- L(t), M(t) and S(t): Box-cox power, median and CV respectively
- y: Individual BMI or height value
- SD3pos: is the cut-off 3 SD calculated at t (age) by LMS method:  
 $SD3pos = M(t)[1 + L(t) * S(t) * (3)]^{1/L(t)}$
- SD3neg: is the cut-off -3 SD calculated at t by the LMS method:  
 $SD3neg = M(t)[1 + L(t) * S(t) * (-3)]^{1/L(t)}$
- SD23pos: is the difference between the cut-offs 3 SD and 2 SD calculated at t by LMS method:  
 $SD23pos = M(t)[1 + L(t) * S(t) * (3)]^{1/L(t)} - M(t)[1 + L(t) * S(t) * (2)]^{1/L(t)}$
- SD23neg: is the difference between the cut-offs -2 SD and -3 SD calculated at t by LMS method:  
 $SD23neg = M(t)[1 + L(t) * S(t) * (-2)]^{1/L(t)} - M(t)[1 + L(t) * S(t) * (-3)]^{1/L(t)}$

To illustrate the procedure, an example with BMI-for-age for boys is provided below and displayed in [Figure 6-1](#).

[figure not shown]

Figure 6-1 Examples of children/adolescents ranked according to the 2007 WHO BMI-for-age reference.

Statistical Analysis Plan  
 Trial ID: NN8022-4179  
 UTN: U1111-1162-7884  
 EudraCT No: 2014-004415-37

~~CONFIDENTIAL~~

Date: 14 December 2020  
 Version: 1.0  
 Status: Final  
 Page: 31 of 36

Novo Nordisk

Child 1: 11-year-old boy with BMI=30

$L=1.7862$   $M=16.9392$   $S=0.11070$

$$Z = \frac{[30.0/16.9392]^{(-1.7862)} - 1}{0.11070 * (-1.7862)} = 3.24 > 3$$

$$SD3 = 16.9392 * [1 + (-1.7862) * 0.11070 * (3)]^{1/(-1.7862)} = 28.03$$

$$SD2 = 16.9392 * [1 + (-1.7862) * 0.11070 * (2)]^{1/(-1.7862)} = 22.45$$

$$SD23 = 28.03 - 22.45 = 5.58$$

$$Z_{ind}^* = 3 + (30 - 28.03/5.58) = 3.35 \text{ (BMI SDS)}$$

Similar calculation will be done for height SDS.

### 6.3.1.2 C-SSRS questionnaire

The Columbia-Suicide Severity Rating Scale questionnaire is used for part A to assess the subject's mental state. It contains two sets of questions; one meant for the screening/randomisation visit (C-SSRS-01; baseline) and the other for the rest of the visits (C-SSRS-02; since last visit). At screening/randomisation, the questionnaire is part of the exclusion criteria (suicidal behavior, previous suicide attempts). During the trial, the questionnaire is used to evaluate the subject's mental status between visits. The first part of the questionnaire is to build up around 'yes/no' questions, which depending on the answers trigger other parts of the questionnaire

### 6.3.1.3 PHQ-9 questionnaire

The Patient Health Questionnaire 9 is used for part A to assess the mental health of the subject. PHQ-9 is done throughout the trial period. It contains 9 questions which are answered with a categorical rating (not at all, several days, more than half the days, nearly every day) translated directly into a number (0-3). The numbers are summed at the bottom of the questionnaire by the investigator. Similar to C-SSRS-01, this questionnaire is used at screening/randomisation as part of the exclusion criteria, i.e., if the total score is  $\geq 15$  then the subject should be excluded from the trial.

### 6.3.1.4 Hyperphagia questionnaire

Hyperphagia, a characteristic of patients with PWS, will be assessed using the hyperphagia questionnaire. It contains 13 questions. Out of 13 questions 11 questions are categorised into 3 domains (behaviour, drive and severity) scores. 2 questions will be considered as additional questions. The Total score is the sum of all the 3 domain scores.

12 questions out of 13 are answered with a categorical rating, translated directly into a number (1-5). There is one question, "how old was your child when they first showed an increased interest in food?" which will be answered in to number directly.

### 6.3.1.5 New classification of hypoglycaemia

Treatment emergent hypoglycaemic episodes will also be summarised by International Hypoglycaemia Study Group (IHSG) 2017, ADA 2018 and ISPAD 2018 for clinically significant hypoglycaemia (PG confirmed <3.0 mmol/L) (see [Table 6-1](#) for the new classification).

**Table 6-1 New classification of hypoglycaemia**

Level	Glycaemic criteria	Description
Hypoglycaemia alert value (level 1)	< 3.9 mmol/L (70 mg/dL) and $\geq$ 3.0 mmol/L (54 mg/dL)	Sufficiently low for treatment with fast-acting carbohydrate and dose adjustment of glucose-lowering therapy
Clinically significant hypoglycaemia (level 2)	< 3.0 mmol/L (54 mg/dL)	Sufficiently low to indicate serious, clinically important hypoglycaemia
Severe hypoglycaemia (level 3)	No specific glucose threshold	Hypoglycaemia associated with severe cognitive impairment requiring external assistance for recovery
Unclassifiable	Unclassifiable	Episodes which could not be classified according to the above new classifications

Notes: The above terms 'hypoglycaemia alert value' for level 1 and 'clinically significant hypoglycaemia' for level 2 were adapted by Novo Nordisk from IHSG 2017, ADA 2018, ISPAD 2018 recommendations for hypoglycaemia. 'Severe hypoglycaemia' (level 3) term was as defined by ADA 2013 and ISPAD 2018.

## 6.3.2 Analysis Rules

### 6.3.2.1 Visit Windowing

Primary and secondary endpoints analysis is performed at Visit 10 (week 16) and Visit 19 (week 52).

For subjects who prematurely discontinues trial product or subject and/or the subject's LAR(s) withdraw consent, the investigator must aim to undertake procedures similar to those for the end of treatment (V19) as soon as possible and the follow up visit (V20) two weeks later.

The subjects were asked to attend additional visits depending on when the trial product discontinuation takes place during the trial:

- If trial product is discontinued between V3 and V9, the subject should attend V10x (16 weeks after V3) and V19x (52 weeks ( $\pm$  5 days) after V3).
- If trial product is discontinued between V11 and V19, the subject should attend V19x (52 weeks ( $\pm$  5 days) after V3).

The end of double-blind treatment (V10) and end of treatment (V19) collected for prematurely discontinued subject and withdrawn subjects did not exactly taken place in respective endpoint

weeks (i.e., at week 16 and week 52). Hence these records will be reallocated to the respective weeks based on analysis day on when the assessments are done by visit windowing concept.

### 6.3.2.2 Visits windows

Generally, visit-windows will be used for the data that is summarized by visit; they are based on the study evaluation schedule and comprise a set of days around the nominal visit day. For any assessment, there are the protocol defined scheduled visits around which visit windows were created to cover the complete range of days within the study.

In 4179 the visit windowing will be done only for V10 and V19 visits for prematurely discontinued/withdrawn subjects.

The visit windows are shown in [Table 6-2](#).

In this table, the days are counted since the date of randomization for both safety and efficacy assessments. These visit windows apply to measurements taken at every visit. For assessments collected less often different visit windows will be applied as detailed below.

When visit windows are used, all visits will be re-aligned, i.e., they will be mapped into one of the visit windows. For example, if the Week 4 visit of a subject is delayed and occurs on Day 46 instead of on Day 29, it will be re-aligned to visit window Week 8. In the case of major deviations from the visit schedule, or due to unscheduled visits, several assessments of a subject may fall in a particular visit window (either scheduled or unscheduled). Statistical approaches to handle multiple assessments in a given visit window are specified below.

In general, if two consecutive visits  $V_t$  and  $V_s$  are  $x$  days apart, the upper limit of the visit window for  $V_t$  will be  $V_t+x/2$  and the lower limit for the visit  $V_s$  will be  $V_s-x/2$  (if  $x$  is even, the lower limit for  $V_s$  will be  $V_s-x/2+1$ , and the upper limit for  $V_t$  will be  $V_t+x/2$ ). The algorithm needs to ensure that visit windows are not overlapping and that there are no gaps, such that each assessment can be uniquely allocated to one visit window, e.g., if Week 8 visit is scheduled for day 57, Week 12 is scheduled at Day 85 and Week 16 is scheduled at Day 113, then the visit window for week 12 extends from Day 79 to Day 106.

Note: The lower limit of first visit will be assigned with -999 which accommodate all assessments occurred before the scheduled day.

The upper limit of last visit will be assigned with 999 which accommodate all assessments occurred after the scheduled day.

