**6.3.2.4 For parameters which are collected at ‘x’ visits:**

For premature discontinued subjects a parameter such as ‘BODY WEIGHT’, ‘HEIGHT’ is collected at additional visits like 10x and 19x, hence if the visit reallocation for these parameters and related parameters such as ‘BMI’, ‘BMI SDS’ are reallocated to x visit instead of normal visit (i.e., visits 10 and 19). Other parameters are reallocated to normal visits.

Note: Withdrawal subjects are reallocated to normal visits.

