**6.3.3 Analysis eligible records:**

If the records are reallocated to the visit which is already collected, then the collected visit record is used for analysis instead of record which is reallocated to that visit.

if the subjects have records for both normal visit (Visit 10 (week 16) and x visit Visit 10x (week 16) then the records which are reallocated are not eligible for analysis.

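### The midpoint rule in SAP 6.3.2.2 and its Table 6-2 give different week-16 and week-52 windows, and the two worked examples follow different sources; the effect is small and may be nil

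*SAP*

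**What the plan says.** SAP 6.3.2.2 contains four statements about the windows.

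- **A rule.** For consecutive visits x "days apart, the upper limit of the visit window for" the earlier visit is its scheduled day plus x/2. When x is even, the lower limit of the later visit is its scheduled day minus x/2 plus 1.
- **A first example.** If a Week 4 visit "occurs on Day 46 instead of on Day 29, it will be re-aligned to visit window Week 8".
- **A second example, attached to the rule.** With weeks 8, 12 and 16 on Days 57, 85 and 113, "then the visit window for week 12 extends from Day 79 to Day 106".
- **A table.** The text sends the reader to Table 6-2 for the windows. SAP 6.3.2.3 treats the Table 6-2 windows as the definition and pools them into Table 6-3 for height.

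The scope is narrow: "the visit windowing will be done only for V10 and V19 visits for prematurely discontinued/withdrawn subjects". For subjects who stop early, BMI and BMI SDS records "are reallocated to x visit instead of normal visit" (SAP 6.3.2.4). If the target visit was actually collected, "then the collected visit record is used for analysis instead of record which is reallocated to that visit" (SAP 6.3.3).

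**The concern.** The rule and the table cannot both be applied, and each example supports a different one. Two programmers working from this SAP could assign the same end-of-treatment record to different weeks.

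This matters because windowing decides whether such a record is a co-primary value. Take a BMI SDS record on Day 100-106 with no collected V10 or V10x. Under the rule it is the week-16 value. Under Table 6-2 it goes to week 12, and under Table 6-3 to Visit 3. In both of those cases week 16 is missing and is imputed from placebo (SAP 5.3.2.2). The same applies at week 52 to Day 352-358 and Day 372. If the question is settled after treatment codes are known, it becomes a post-hoc choice on a co-primary endpoint.

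**Working it through.** **Inputs.** Scheduled days and printed windows are from SAP Table 6-2. The rule and examples are from SAP 6.3.2.2. The sample size of 57 (38 and 19), the SD of 0.25, the difference of -0.23, and withdrawal of 10% by week 16 and 20% by week 52 are from protocol 17.1.

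**Where rule and table agree.** For weekly visits x = 7. Rounding x/2 = 3.5 inward gives V4 = 5-11, V5 = 12-18, V6 = 19-25 and V7 from Day 26, all as printed.

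**Where they part.** For x = 28, upper = day + 14 and lower = day - 14 + 1 = day - 13. Between V19 (Day 365) and V20 (Day 379) x = 14, so V19 ends at 365 + 7 = 372 and V20 starts at 379 - 7 + 1 = 373.

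| Visit | Scheduled day | Rule | Table 6-2 |
|---|---|---|---|
| Week 4 | 29 | 26-43 | 26-50 |
| Week 8 | 57 | 44-71 | 51-78 |
| Week 12 | 85 | 72-99 | 79-106 |
| Week 16 | 113 | 100-127 | 107-134 |
| Week 52 | 365 | 352-372 | 359-371 |

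Day 46 lies in week 8 by the rule (44-71) and in week 4 by the table (26-50). The first example therefore follows the rule and the second follows the table.

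Other readings of the rule do not rescue the table. Without the +1, weeks 12, 16 and 52 become 71-99, 99-127 and 351-372. With the one-day adjustment moved to the upper limit, they become 71-98, 99-126 and 351-371.

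**Likely source.** All 12 printed lower limits from week 8 to week 52 equal the scheduled day minus 6 (51 - 57, 79 - 85, ..., 359 - 365). The rule gives that result for x = 14: -7 + 1 = -6. These visits are 28 days apart.

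**Table 6-3.** Pooling the rule's windows gives V3 = -3 to 99, V10 = 100-183, V13 = 184-267, V16 = 268-351 and V19 from 352. The table prints -2 to 106, 107-190, 191-274, 275-358 and 359-371.

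**Days that matter for the endpoints.**
- Days 100-106, 352-358 and 372 count as week 16 or week 52 under the rule and under neither table.
- Days 128-134 (if Table 6-2 governs BMI SDS) or 184-190 (if Table 6-3 does) count as week 16 in print but not under the rule. This matters only if V10 is missing.
- Visits within the protocol's ±5 days (108-118 and 360-370) are classified the same either way.

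**Expected number of records.** Assume 10% of 57 = 5.7 subjects stop evenly over the first 112 days and a further 5.7 over the next 252, each with an end-of-treatment record.
- Day 100-106: 5.7/112 × 7 = 0.356
- Day 352-358: 5.7/252 × 7 = 0.158
- Day 372: 5.7/252 × 1 = 0.023

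The total is 0.36 if every V19x is attended and 0.54 if none is. Liraglutide carries 2/3 of these, so the Poisson chance of at least one liraglutide record is 1 - exp(-0.356 × 2/3) = 21% to 1 - exp(-0.537 × 2/3) = 30%.

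**Shift per liraglutide record.** Replacing a value at -0.23 by a placebo-like one moves the difference by 0.23/38 = 0.006. The planned standard error is 0.25 × √(1/38 + 1/19) = 0.070, and 0.0061/0.0702 = 9%.

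**The case against.** The best reply is that the table governs. The section points to it for the windows, 6.3.2.3 treats it as their definition, and the formula is introduced only as a general statement. The V10 and V19 windows are explicit numbers without overlap, so a programmer can apply them and ignore the formula. This stands as far as it goes. A reader might infer that the plan leaves the week-16 and week-52 windows undefined, or that the printed ones are certainly wrong. The documents support neither. The minus-6 pattern suggests a calculation slip but does not prove one. The contradiction nevertheless remains if the table governs, because the Day-46 example and the rule then both conflict with it.

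A second reply is that protections elsewhere shrink the effect. Collected visits take precedence, and protocol 8.1.8 asks subjects who stop to attend V10x and V19x. This also stands in part. The main contribution, Day 100-106, needs V10x to be absent. Protocol 8.1.8 and SAP 6.3.2.1 request x visits after stops between V3 and V9 and between V11 and V19. Read literally, they omit a stop between V9 and V10. That is a follow-up question rather than a windowing error, and if V10x is attended the contribution disappears. For withdrawal of consent, however, protocol 8.1.9 requests no x visit, so a reallocated record may be the only one.

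The screening rows also depart from the rule, and the note that "The lower limit of first visit will be assigned with -999" is not reflected in Visit 1's printed start at Day -15. A reader might add these to the case. They assign no V10 or V19 record, so they carry no weight for the endpoints.

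**Conclusion.** SAP 6.3.2.2 contradicts itself on its own figures, and Table 6-3 inherits the printed limits. Table 6-2 is the more natural governing source, but no choice of source makes the rule, both examples and the table agree.

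The consequence is limited to discontinued or withdrawn subjects with a record on one of the days listed above and no collected week-16 or week-52 visit. The documents give no count of such records. The estimates of 0.36 to 0.54 records, and of a 21-30% chance of at least one on liraglutide, rest on evenly spread withdrawal at the planned rates, attended end-of-treatment visits with weight and height, and no V10x after a stop between V9 and V10. A shift of about 0.006 per liraglutide record is 2.6% of the planned -0.23.

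A reader might infer that the co-primary result is at risk. The figures do not support that: the effect is small and may be nil. The correction is still worth making, because these windows decide which records enter a co-primary analysis.

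A related gap is that the SAP does not say which table governs BMI SDS. Since "For assessments collected less often different visit windows will be applied as detailed below" and BMI SDS needs height, Table 6-3 is the natural reading, but it is not stated.

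**What to change.** Before treatment-coded analysis, make the rule, both examples and Tables 6-2 and 6-3 give one set of windows. Either route works.

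- **(a) Keep the tables.** State that the printed tables govern, replace the midpoint formula with one that reproduces them, and change the Day-46 example to Week 4. This leaves the printed endpoint windows unchanged.
- **(b) Keep the rule.** Recompute Table 6-2 (week 16 = 100-127, week 52 = 352-372, V20 from 373, with the other rows to match) and Table 6-3 (V3 = -3 to 99, V10 = 100-183, V13 = 184-267, V16 = 268-351, V19 from 352). Change the week-12 example to Day 72-99.

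Under either route, apply the -999 and 999 end limits consistently, including to V19 as the last visit in Table 6-3, or state otherwise. As printed, a height after Day 371 has no window there. Also name the table that governs BMI and BMI SDS.

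The cost is a text correction to one SAP section and its tables, with matching derivation code. No new data are needed.
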